4.2 Secondary Objectives

1. For those subjects who participated in the Comparator study of ⁶⁸Ga-DOTATOC versus Octreoscan + conventional imaging using high-resolution, contrast-enhanced CT or MRI (IRB# 201212736), the intent is to determine response to therapy of lesions identified by ⁶⁸Ga-DOTATOC PET/CT but not identified on Octreoscan as a confirmatory measure of true positivity of the Ga-68 DOTATOC avid lesion.
2. Determine if Standard Uptake Value (SUV) on initial ⁶⁸Ga-DOTATOC/TATE PET imaging correlates with SSTR2 expression as measured by quantitative messenger RNA (qPCR) or immunohistochemistry (IHC) on the diagnostic biopsy specimen.

5.0 Eligibility Criteria

5.1 Inclusion Criteria

1. Disease not amenable to standard treatment (nonresectable or disease present after one or more surgeries and/or Sandostatin treatment) or subject has failed existing first line chemotherapy, biologic therapy, targeted agent therapy or radiation therapy.
2. Participation in Iowa Neuroendocrine Tumor Registry.

3. A pathologically confirmed (histology or cytology) malignant neoplasm with at least one target lesion that is confirmed by conventional imaging and is determined to express somatostatin receptors by ⁶⁸Ga-DOTATOC (TATE) PET within 6 months prior to treatment with ⁹⁰Y-DOTATOC.
4. The target lesion is one that either has never received external beam radiation or has been previously irradiated and has since demonstrated progression. Any local irradiation of the target lesion or any non-target lesions via external beam, conformal or stereotactic radiation treatments must have occurred more than 4 weeks prior to study drug administration. Any full cranial-spinal radiation, whether or not a target lesion is included in the field, must have occurred more than 3 months prior to study drug administration.
5. Life expectancy \geq 2 months at the time of study drug administration.
6. Archival tissue from a previous biopsy will be required.
7. Age \geq 6 months-90 years at the time of study drug administration.
8. Performance status as determined by Karnofsky \geq 60 or Lansky Play Scale \geq 60% at the time of study drug administration.
9. Completion of Norfolk Quality of Life Questionnaire.
10. Within 7-10 days of study drug administration, patients must have normal organ and marrow function as defined below:
 - absolute neutrophil count \geq 1000/mm³
 - Platelets \geq 90,000/mm³
 - total bilirubin <3X ULN for age
 - AST(SGOT) & ALT(SGPT) \leq 10X institutional upper limit of normal for age
 - Urinalysis no greater than 1+ hematuria or proteinuria
Adults(age18 or >): Serum creatinine \leq 1.2 mg/dl; if serum creatinine is >1.2 mg/dL, nuclear GFR will be measured.
GFR will need to be \geq 80 ml/min/1.73m² for subjects \leq 40 years old,
 - Renal function* \geq 70 ml/min/1.73m² for subjects between 41-50;
 \geq 60 ml/min/1.73m² for subjects between 51-60;
 \geq 50 ml/min/1.73m² for subjects > 60 years old.

Children(age <18): nuclear GFR \geq 80 mL/min/1.73 m²
- * Renal function criteria based on our previous experience with ⁹⁰Y-DOTATOC therapy and known changes in GFR with age^{13,21,33-35}
11. The effects of ⁹⁰Y-DOTA-tyr³-Octreotide on the developing human fetus are unknown. For this reason and because Class C agents are known to be teratogenic, women and men of child-bearing potential must agree to use adequate contraception (hormonal or barrier method of birth control) prior to study entry and for the duration of study participation. Should a woman become pregnant or suspect she is pregnant while participating in this study, she should inform her treating physician immediately.
12. Ability to understand and the willingness to sign a written informed consent document.

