1.4 Somatostatin Receptor Targeted Therapy

Known as peptide receptor radionuclide therapy (PRRT), this molecularly targeted internal radiation has been utilized in Europe for nearly 20 years. The two main radiopharmaceutical agents are ^{90}Y -DOTATOC and ^{177}Lu -DOTATATE, both targeting sstr2. The response rates are very similar with very few complete responses, 20-30% partial responses, and greater than 50% stable disease among patients who have progressed on other therapies^{22,23}. The time to progression following PRRT, for these patients with progressive metastatic neuroendocrine tumors has been 36-48 months compared to 5-7 months with everolimus or sunitinib^{24,25}.

The normal organ at greatest risk for toxicity with ^{90}Y -DOTATOC is the kidney^{21,23,26,27}. In our previous Phase II trial in adults and our Phase I trial in children, we were able to decrease renal toxicity with amino acid infusion and hydration^{13,21,28}. This trial is designed to utilize dosimetry to maximize radiation dose to tumor while minimizing renal toxicity.

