7.0 Calendar of Tests and Procedures

Calendar of Tests and Procedures									
Test	Base line ⁶	C1D1 ⁷	C1D2	C2 D1	C2D2	C3D1	C3D2	3-4 Month Followup ^{8, 11}	6-9 Month Followup
Physical Exam	X	X		X		X		X	X
Medical history/treatment history	X	X							
Vital signs ¹	X	X	X	X	X	X	X	X	X
Medication list	X	X		X		X		X	X
GFR if indicated ²	X	X		X		X		X ¹²	X
Blood Tests ³	X	X	X ¹⁴	X	X ¹⁴	X	X ¹⁴	X	X
QOL questionnaire	X	X						X ¹³	
Pregnancy Test ⁴	X	X ⁹	X ⁹	X	X ⁹	X	X ⁹		
⁶⁸ Ga-DOTATOC (TATE) PET/CT	X								X
Diagnostic CT or MRI	X							X	X
⁹⁰ Y-DOTATOC Therapy (& Amino Acids)			X		X		X		
Skin assessment ¹⁵			X		X		X		
Dosimetry (blood & imaging)			X		X		X		
Adverse Event Assessment	X ⁵	X	X	X		X		X	X
Fluid diary ¹¹		X	X	X	X	X	X		

1. temp, pulse, respirs, b/p, weight. Height at baseline only. Weight at baseline and Day 1 of each cycle.

2. required for children(<18 years). Required for adults (18 and older) if serum creatinine >1.2mg/dl. If required at baseline for patient, then all subsequent time points require nuclear GFR also.

3. blood tests include: CBC/diff, AST, ALT, creatinine, plus urinalysis at baseline only and T.Bili at baseline only.

4. required for females of child bearing potential only

5. Documentation of baseline symptoms

6. All baseline evaluations within 30 days of first ⁹⁰Y-DOTATOC dose except blood tests need to be within 10 days and ⁶⁸Ga-DOTATOC/TATE PET/CT needs to be within 6 months of first ⁹⁰Y-DOTATOC infusion. The diagnostic scans need to be within 120 days of the first ⁹⁰Y-DOTATOC infusion.

7. events only repeated prior to treatment 1 if they fall outside of the baseline windows noted in footnote 6.

8. Patients who discontinue dosing of ⁹⁰Y-DOTATOC early and who have received at least 1 dose of ⁹⁰Y-DOTATOC are also required to complete follow up appointments per calendar

9. repeat testing can be point of care urine pregnancy test done in Nuclear Medicine.
10. Patients will be instructed to have fluid intake of 1.5 liters Day 1 and 2 liters/day on Days 3 & 4.
11. 3-4 month follow up procedures may be performed by patient's local MD.
12. If GFR is indicated, patients will be required to return to UIHC.
13. If patient does not return to UIHC for F/U, QOL may be mailed or e-mailed to patient.
14. Electrolytes will be drawn during the last hour of amino acid infusion.
15. The skin at the site of the infusion will be assessed by clinic visit or phone at 3-5 days following each infusion of amino acids.

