10	Y / N Within 7-10 days of study drug administration, patients must have normal organ and marrow function as defined below: 
 
 absolute neutrophil count	\geq1000/mm³	
 
 Platelets	\geq90,000/mm³	
 
 total bilirubin	<3X ULN for age	
 
 AST(SGOT) & ALT(SGPT)	\leq10X institutional upper limit of normal for age	
 
 Urinalysis	no greater than 1+ hematuria or proteinuria	
 
 
Adults(age 18 or >): Serum creatinine \leq 1.2 mg/dl; if serum creatinine is >1.2 mg/dL,
 
GFR will need to be \geq 80 ml/min/1.73m² for subjects \leq40 years old,
 Renal function 
\geq 70 ml/min/1.73m² for subjects between 41-50;
 
\geq 60 ml/min/1.73m² for subjects between 51-60;
 
\geq 50 ml/min/1.73m² for subjects > 60 years old.
 
Children(age <18): creatinine and nuclear GFR \geq 80 mL/min/1.73 m²
	absolute neutrophil count	\geq 1000/mm ³	Platelets	\geq 90,000/mm ³	total bilirubin	<3X ULN for age	AST(SGOT) & ALT(SGPT)	\leq 10X institutional upper limit of normal for age	Urinalysis	no greater than 1+ hematuria or proteinuria
absolute neutrophil count	\geq 1000/mm ³										
Platelets	\geq 90,000/mm ³										
total bilirubin	<3X ULN for age										
AST(SGOT) & ALT(SGPT)	\leq 10X institutional upper limit of normal for age										
Urinalysis	no greater than 1+ hematuria or proteinuria										
11	Y / N Negative pregnancy test. The effects of ⁹⁰ Y-DOTA-tyr ³ -Octreotide on the developing human fetus are unknown. For this reason and because Class C agents are known to be teratogenic, women and men of child-bearing potential must agree to use adequate contraception (hormonal or barrier method of birth control) prior to study entry and for the duration of study participation. Should a woman become pregnant or suspect she is pregnant while participating in this study, she should inform her treating physician immediately.										

12 Y / N Ability to understand and the willingness to sign a written informed consent document.

**Exclusion
Criteria**

- 1 Y / N Pregnant women.

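### Eligibility requires nuclear GFR within 10 days of dosing, but the calendar allows 30 days and is inconsistent on whether a GFR 11–30 days old must be repeated before Cycle 1

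*Combined protocol and SAP*

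**What the plan says.** **Eligibility.** Section 5.1, item 10, opens "Within 7-10 days of study drug administration, patients must have normal organ and marrow function as defined below". The renal limits sit under that sentence. Children need a nuclear GFR of at least 80 mL/min/1.73 m². Adults qualify on creatinine up to 1.2 mg/dL; above that, a nuclear GFR is measured against age-specific limits of 50 to 80. Item 10 of the inclusion form in Appendix III has the same opening. Its paediatric line begins "Children(age <18): creatinine and nuclear GFR", with no numerical limit for creatinine.

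**Calendar (section 7.0).** Nuclear GFR has its own row, with entries at baseline and at Cycle 1 Day 1. Four footnotes bear on it:

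- Footnote 6 sets the default: "All baseline evaluations within 30 days of first" dose. The exceptions are blood tests ("dose except blood tests need to be within 10 days and"), the PET/CT (6 months) and the diagnostic scans (120 days).
- Footnote 3 defines the blood tests: "blood tests include: CBC/diff, AST, ALT, creatinine, plus urinalysis at baseline only", with total bilirubin also at baseline. GFR is not listed.
- Footnote 7, attached to the Cycle 1 Day 1 column, reads "events only repeated prior to treatment 1 if they fall outside of the baseline windows noted in footnote 6".
- Footnote 2, attached to the GFR row, says who needs the test: "required for children(<18 years). Required for adults (18 and older) if serum creatinine" exceeds 1.2 mg/dL. Its last sentence adds that a patient who needed nuclear GFR at baseline needs it at every later time point.

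**Schemas.** The schema at the front of the protocol and the table in section 6.0 both list GFR on Cycle 1 Day 1, with no window or condition.

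**The concern.** Two parts of the protocol set different maximum ages for the same safety test, and the calendar is the part that schedules it. Staff who follow footnotes 6 and 7 could leave a three-week-old GFR in place. Staff who follow footnote 2 or the schemas would repeat it the day before dosing. Only the second course meets item 10.

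The test matters because section 1.4 names the kidney: "The normal organ at greatest risk for toxicity with" this drug. For children, nuclear GFR is the only renal-function measure in item 10 with a numerical limit, so a recent creatinine cannot stand in for it. At stake is whether renal eligibility rests on a value of the age the protocol intends. The design's operating characteristics are not involved.

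**Working it through.** The plan states no figure to reproduce. The check compares the stated windows.

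**Step 1. Which calendar window covers nuclear GFR?** It is not in footnote 3's list, it has its own row, and section 10.1 describes it as a scan. None of footnote 6's three exceptions fits, so the 30-day default applies.

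**Step 2. Compare the outer limits.**

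| Source | Oldest GFR accepted at first dose |
|---|---|
| Section 5.1 item 10; Appendix III form item 10 | 10 days |
| Section 7.0, footnote 6 | 30 days |

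Ratio: 30 / 10 = 3. Ages that pass the calendar window and fail eligibility: 11 to 30 days, or 30 − 10 = 20 day values. If 7 rather than 10 is taken as the outer limit, the ages are 8 to 30 days, or 30 − 7 = 23 day values. These are ages of a test, not a share of patients.

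**Step 3. Follow a child whose GFR was done on day −20.**

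| Rule | Result |
|---|---|
| Footnote 6 | 20 ≤ 30: inside the window |
| Footnote 7 | Inside the window, so no repeat is called for |
| Footnote 2, last sentence | Cycle 1 Day 1 follows baseline, so GFR is required again |
| Schema and section 6.0 table | GFR listed on Cycle 1 Day 1 |
| Item 10 and the form | 20 > 10: fails unless repeated |

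Footnotes 2 and 7 give opposite instructions for this child, and no text says which prevails.

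**Step 4. Who is affected?** Adults with creatinine up to 1.2 mg/dL qualify on a blood test whose limit is 10 days in both places. Adults whose GFR is prompted by that recent creatinine have a recent GFR. This leaves children, and adults above 1.2 mg/dL who rely on an earlier GFR. The documents give neither the number of children nor the usual timing of GFR tests. The count could be none (every GFR within 10 days) or, at most, every child plus those adults.

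**Step 5. Apply the amended footnote 6.** A day −20 GFR now falls outside its window (20 > 10), so footnote 7 calls for a repeat. Done on Cycle 1 Day 1 with dosing on Day 2, the new value is 2 − 1 = 1 day old, within 10.

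**The case against.** The strongest reply is that the rules are cumulative. Footnote 6 sets an outer scheduling limit and does not authorise dosing; item 10 does the gatekeeping, and a GFR within 10 days meets both. Footnote 2 is specific to GFR while footnote 7 covers a whole column, so the specific rule could reasonably be preferred, and the schemas agree with it. Other protections exist:

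- Creatinine must be within 10 days.
- The investigator signs a form carrying the eligibility window, and the completed checklist goes into OnCore for ongoing review (Appendix II). The 25% minimum in that appendix concerns monitoring of research records and does not limit the checklist upload.
- Section 5.2 excludes surgery, other investigational drugs and chemotherapy within 4 weeks of dosing, so little intervening treatment is possible over most of the 11–30 day span.
- Section 10.1 limits renal dose to 23 Gy by dosimetry.

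Most of this stands, and it is why the point is minor. It does not remove the conflict: no text ranks footnote 2 above footnote 7, or item 10 above the calendar, and a check at the eligibility form can come late, when the remedy is a hurried scan or a delayed dose.

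A reader might infer that the calendar plainly forbids repeating an 11–30 day old GFR, so that children will be dosed on values that fail eligibility. The documents do not support that. Footnote 2's last sentence and both schemas point to a repeat, and the form would catch many of the remaining cases.

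A reader might also infer that section 10.1 leaves its GFR reference value undefined. The baseline-visit value is the natural reading, and a defect in the current text is not shown.

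**Conclusion.** The inconsistency is real and minor. For subjects who need nuclear GFR, eligibility allows 10 days and footnote 6 allows 30, and the calendar's own footnotes disagree on whether a test 11 to 30 days old must be repeated. The likely consequence is a late repeat test or an eligibility deviation, mainly in children. The number of subjects cannot be derived and may be zero.

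The conclusion rests on two readings: that 10 days is the outer limit of item 10's window (no reading of it reaches 30), and that nuclear GFR is not a blood test in footnote 3's sense. Confidence is moderate, because footnote 2 can fairly be read as already requiring the repeat.

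**What to change.** Widen the 10-day exception in footnote 6 of section 7.0 to read: *blood tests and, if indicated, nuclear GFR need to be within 10 days*. Footnote 7 then triggers a Cycle 1 Day 1 repeat for any older GFR, in agreement with item 10 and the form, neither of which needs to change. Footnotes 2 and 7 may still differ for a GFR of 10 days or less, but either course then meets eligibility.

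The cost is a few words. Some GFRs must be timed later or repeated, which for a child can mean one extra nuclear medicine procedure, but item 10 already requires this.

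Optional housekeeping: one sentence in section 10.1 naming which pre-dose GFR is the reference for the 30%, 90% and 50% rules if two exist. The baseline-visit value or the last value before the first dose would serve.

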5.2 Exclusion Criteria

1. Pregnant women are excluded from this study because ⁹⁰Y-DOTATOC is a *Class C* agent with potential teratogenic or abortifacient effects.
2. Because there is an unknown but potential risk for adverse events in nursing infants secondary to treatment of the mother with ⁹⁰Y-DOTATOC, breastfeeding should be discontinued until 6 weeks after the last administration of study drug.
3. Surgery within 4 weeks of study drug administration.
4. External beam radiation to both kidneys (scatter doses of <500 cGy to a single kidney or radiation to < 50% of a single kidney is acceptable).

5. Prior PRRT with ⁹⁰Y-DOTATOC (TATE) or ¹⁷⁷Lu-DOTATOC (TATE) or ¹³¹I-MIBG therapy for this malignancy.
6. Another investigational drug within 4 weeks of study drug administration.
7. Concurrent, malignant disease for which patient is on active therapy.
8. Another significant medical, psychiatric, or surgical condition which is currently uncontrolled by treatment and which would likely affect the subject's ability to complete this protocol.
9. Any subject for whom, in the opinion of their physician, a 12-hour discontinuation of somatostatin analogue therapy represents a health risk. Also subjects who have received SandostatinLAR in the past 28 days or long-acting lanreotide within the past 8 weeks are excluded. Subjects may be maintained on short acting octreotide during the time from last injection of long-acting somatostatin analogue until 12 hrs prior to injection of study drug. Known antibodies to Octreotide, Lanreotide, or DOTATOC or history of allergic reactions attributed to compounds of similar chemical or biologic composition to ⁹⁰Y-DOTATOC.
10. Patients who have had chemotherapy within 4 weeks (6 weeks for nitrosoureas or mitomycin C) of study drug administration or those who have not recovered from adverse events due to agents administered more than 4 weeks earlier.
11. Uncontrolled illness including, but not limited to ongoing or active infection, symptomatic congestive heart failure, unstable angina pectoris, cardiac arrhythmia, or psychiatric illness/social situations that would limit compliance with study requirements.
12. Subject weighs more than 450 pounds. (Subjects who weigh more than 450 pounds will not be able to fit inside the imaging machines.)
13. Inability to lie still for the entire imaging time (due to cough, severe arthritis, etc.)

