6.0 Imaging and Treatment Plan

**Phase II,
Dosimetry-Guided, Peptide Receptor Radiotherapy (PRRT) with
⁹⁰Y-DOTA-tyr³-Octreotide (⁹⁰Y-DOTATOC) in Children and Adults
with Neuroendocrine and other Somatostatin Receptor Expressing Tumors**

Treatment Cycles and Followup		Imaging and Treatment Schedule	Initial ⁹⁰ Y-DOTATOC Dose	Cumulative ⁹⁰ Y-DOTATOC Dose	Cumulative Renal Radiation
Cycle 1 Week 1	Day 1	Physical exam with height, weight, vitals, labs, list, GFR, pregnancy test; QOL questionnaire Start 18 hrs IV/PO fluids			
	Day 2	⁹⁰ Y-DOTATOC + IV amino acids Continue IV/PO fluids for 48 hrs	50 mCi/m ² in children; 120 mCi in adults	120 mCi maximum	
	Day 4	⁹⁰ Y-DOTATOC PET/CT			
Cycle 2 Week 7-9	Day 1	Physical exam with height, weight, vitals, labs, med list, GFR, pregnancy test Start 18 hrs IV/PO fluids			
	Day 2	⁹⁰ Y-DOTATOC + IV amino acids Continue IV/PO fluids for 48 hrs	Dosimetry determined	270 mCi maximum	
	Day 4	⁹⁰ Y-DOTATOC PET/CT			
Cycle 3 Week 13-17	Day 1	Physical exam with height, weight, vitals, labs, list, GFR, pregnancy test Start 18 hrs IV/PO fluids			
	Days 2-3	⁹⁰ Y-DOTATOC + IV amino acids Continue IV/PO fluids for 48 hrs	Dosimetry determined	420 mCi maximum	≤ 23 Gy
FU	3 months after treatment 3	Physical exam with height, weight, vitals, labs, med list, GFR; QOL questionnaire, diagnostic CT (MRI)			
	6-9 months after treatment 3	Physical exam with height, weight, vitals, labs, med list, GFR; diagnostic CT (MRI) ⁶⁸ Ga-DOTATOC PET/CT;			

Treatment consists of 3 cycles, 6-8 weeks apart. Cycle 1 dose is fixed. Cycles 2 and 3 doses will be determined by dosimetry-based calculation of renal doses from previous cycles; total renal dose ≤ 23Gy.

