6.1 Delivery of Therapeutic Infusion

⁹⁰Y-DOTA-tyr³-Octreotide and amino acid infusions will be administered on Day 2 of each treatment cycle. A large IV, either 20 gauge peripheral IV or a PICC line, will be inserted to provide free flow of the hyperosmolar amino acid solution, thus avoiding local inflammation with risk of blistering. Amino acid infusion will begin 30 min prior to infusion of ⁹⁰Y-DOTATOC and continue 3.5 hrs after infusion of radiotherapeutic drug. If rate of amino acid infusion is decreased due to nausea, the length of infusion

may be longer than 3.5 hrs. There will be rescue Sandostatin available (subcutaneous bolus of 200 µgm (200 µgm/mL)) in case of carcinoid crisis after ⁹⁰Y-DOTATOC infusion has been completed.

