10.3 Concomitant Therapy

The subject may not receive any other approved or investigational anti-neoplastic therapies for the treatment of the refractory somatostatin-receptor positive tumor during the course of the study, excluding somatostatin analogues and bisphosphonates. However, all subjects on somatostatin analogue therapy will discontinue therapy from 12 hours prior to a) injection with ^{68}Ga -DOTATOC, and b) infusion with ^{90}Y -DOTA-tyr³-Octreotide until 12 hours post administration. Subjects who have been on hormonal therapy (other than somatostatin analogues) for ≥ 2 months with SD or PD may continue to receive hormonal therapy during this study. Subjects who initiate another tumor-specific therapy will be discontinued from further treatment with ^{90}Y -DOTA-tyr³-Octreotide. Patients may continue long acting Somatostatin analogues between cycles of ^{90}Y therapy. It should be administered as standard of care after completion of dosimetry imaging for Cycles 1 and 2. Following Cycle 3, it may be given on Day 3 or later. Patients on long acting Lanreotide should have this treatment held until after ^{90}Y treatment Cycle 3. Short acting somatostatin analogue can be used at the discretion of the treating physician to bridge the patient.

All subjects who have received at least one dose of ^{90}Y -DOTA-tyr³-Octreotide must continue into the Long-Term Follow-up Study Period at the point of treatment discontinuation. This is necessary to determine any long-term effects of treatment with ^{90}Y -DOTA-tyr³-Octreotide.

Subjects may receive, at the discretion of the investigator, appropriate medical treatment for medical problems that arise while on study.

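### Exclusion 9 screens for a 12-hour break in somatostatin analogue, but section 10.3 imposes at least 24 hours around each 90Y infusion

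*Combined protocol and SAP*

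**What the plan says.** **Eligibility.** Section 5.2, exclusion 9, turns on the physician's opinion of whether "a 12-hour discontinuation of somatostatin analogue therapy represents a health risk". The same item lets a patient stay on short-acting octreotide "until 12 hrs prior to injection of study drug". It says nothing about when the analogue may restart after dosing. The Appendix III inclusion/exclusion form, which the investigator signs, carries the same 12-hour question and the same pre-dose limit.

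**Treatment.** Section 10.3 states that "all subjects on somatostatin analogue therapy will discontinue therapy from 12 hours prior to" the 68Ga-DOTATOC injection and the 90Y-DOTATOC infusion, and that the hold lasts "until 12 hours post administration".

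**Repetition.** Section 6.0 says: "Treatment consists of 3 cycles, 6-8 weeks apart". The hold therefore recurs at up to three infusions.

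**Related provisions.** On the period after the infusion, section 6.1 says: "There will be rescue Sandostatin available". This is a 200 µg subcutaneous bolus for carcinoid crisis once the 90Y infusion is complete. After directing that lanreotide be held until after Cycle 3, section 10.3 adds: "Short acting somatostatin analogue can be used at the discretion of the treating physician to bridge the patient".

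**The concern.** A safety exclusion should name the exposure that the protocol goes on to impose. This one names half of it or less. The physician is asked about 12 hours, and the patient then goes at least 24 hours without analogue. Someone whose symptoms are controlled on short-acting octreotide, and who could miss 12 hours but not 24, would be correctly recorded as eligible and then exposed to a break that nobody was asked to judge.

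The omitted hours matter. Exclusion 9 requires patients to have been off Sandostatin LAR for 28 days and long-acting lanreotide for 8 weeks (16 weeks on the form). Anyone who needs analogue cover at the first dose is therefore relying on the short-acting drug that is being withheld. Under section 10.3, long-acting analogue in Cycles 1 and 2 is given only after dosimetry imaging, which section 6.2 places at 40 to 56 hours, so no new long-acting dose can be given in the 12 hours after dosing. By stocking a rescue drug for carcinoid crisis after the infusion, the protocol itself recognises that this is a period of risk.

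**Working it through.** No sample-size, power or error-rate figure is involved. The check compares two current sections of the protocol and adds up the hours.

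**Inputs**

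| Quantity | Value | Source |
|---|---|---|
| Break the physician judges | 12 h | 5.2 item 9; Appendix III form item 9 |
| Hold before 90Y infusion | 12 h | 10.3 (also the short-acting limit in 5.2 item 9) |
| Hold after 90Y infusion | 12 h | 10.3 |
| Duration of 90Y infusion, *d* | not stated; *d* > 0 | no figure in the documents |
| Number of infusions | up to 3 | 6.0 |

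**Imposed break per infusion** = pre-dose hold + *d* + post-dose hold = 12 + *d* + 12 = 24 + *d*, so at least 24 h.

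**Ratio to the screened break** = (24 + *d*) / 12, so at least 24 / 12 = 2.

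**Unscreened part per infusion** = (24 + *d*) − 12 = 12 + *d*, so at least 12 h.

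**Over a full course** = 3 × 24 = 72 h at minimum, in three separate breaks of at least 24 h each. The length of the single break is what the physician needs to judge; 72 h is an upper count of occasions and assumes all three cycles are given.

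**Can the two sections be reconciled?**

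- *Reading the 12 hours in exclusion 9 as the whole break.* This fails, because the same item already stops short-acting octreotide 12 h before study drug. That uses up the full 12 h before the infusion starts.
- *Reading the post-dose clause in 10.3 narrowly.* The sentence lists the 68Ga injection as (a) and the 90Y infusion as (b). If the 12-hour post-dose hold applies only to (b), the result for the 90Y infusion is still 24 + *d*.
- *Reading the bridging sentence in 10.3 as an exception.* It follows the direction to hold lanreotide and states no exception to the hold around dosing.

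**The case against.** The case on the other side accepts the text and the arithmetic and disputes the weight.

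- **The post-dose hours are covered by a named rescue drug and dose.** This is true, and it means the hold is not an absolute bar on analogue once a patient becomes ill. But rescue treats a crisis in someone already enrolled. It does not identify beforehand the patient who should not have entered.
- **Clinical judgement recurs.** There is a physical exam and medication review on Day 1 of each cycle, section 8.1 lets the investigator stop treatment, and exclusions 8 and 11 bar uncontrolled illness. These limit repeat exposure after a bad first cycle. They do not screen the first break, and a patient who is well controlled on octreotide is not uncontrolled under exclusion 8 or 11.
- **Bridging is left to the treating physician.** It is, and it shows concern for symptom control around the cycles, but it does not shorten the hold.
- **The harm is not quantified.** This stands. Nothing in the documents shows how many patients tolerate 12 hours but not 24, and the factor of 2 counts hours, not risk. The issue also concerns only patients still using short-acting analogue close to dosing.
- **Section 10.3 might be the part to change.** The documents give no reason for the 12-hour post-dose hold, so the sponsor could shorten it instead. That would also remove the mismatch, but it alters treatment conduct and would need its own justification. Correcting the screening question does not.

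**Conclusion.** The concern holds. Exclusion 9 and the eligibility form screen for a 12-hour interruption, while section 10.3 imposes at least 24 hours at each 90Y infusion. At least 12 hours of each break fall outside the question asked. The result rests only on the current text of 5.2, 10.3 and Appendix III. The unstated infusion time can only lengthen the break.

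The practical weight is moderate. The number of patients affected is unknown, rescue is available after the infusion, and the endpoint, sample size, error rates and analysis are untouched. It should still be corrected, because a criterion meant to protect patients understates what they will undergo and the remedy is simple.

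**What to change.** In section 5.2 item 9 and in item 9 of the Appendix III form, replace the 12-hour interval with *a discontinuation of at least 24 hours (12 hours before to 12 hours after administration)*, so that both match section 10.3. The same edit is a chance to settle the lanreotide washout in that item, which is 8 weeks in section 5.2 and 16 weeks on the form.

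The cost is a wording change in two places and possibly a few more patients screened out; the documents give no basis for a number. Dosing, visits and analysis do not change.
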